APPENDIX I

STUDY CALENDAR

	Pre-Study	Pre-SBRT ⁸	SBRT Treatment ^{9,10}	Follow-Up ⁵ (Post-Radiation Treatment)					
				4-6 weeks	4 mos	6 ³ mos	9 mos	12 ³ mos	Yrs 2-5 Q 3-6 mos
Initial Consult	X								
Demographics	X								
History / Physical Exam	X			X	X	X	X	X	X
Informed consent	X								
Biopsy (confirmed adenocarcinoma)	X								
Labs: CBC, CMP, CA19-9		X ⁶		X	X	X	X	X	X
Post-op complication assessment (appendix 6)				X					
Negative Pregnancy Test ⁷		X							
Seed Placement (EUS, CT, intraoperatively)		X							
Simulation Scan		X							
Radiologic Evaluation (CT)		X		X ²	X	X	X	X	X
QoL Questionnaire		X		X	X ⁴	X	X ⁴	X	X
AE Evaluation	X			X	X	X	X	X	X
Research tubes		X		X ¹¹					

1 - CT pancreas or chest/abdomen/pelvis, as per treating physician, required pre- and post-SBRT.
 2 - If being reevaluated for resection, scans will be conducted at 4-6 weeks or as determined necessary by treating physician.
 3 - It is preferred that patients have the 6MFU and 12MFU evaluation and imaging at the treating institution. Other evaluations may be done at a local center however records must be submitted to SBRT treating facility.
 4 - QoL questionnaires may be completed and returned by mail if preferred.
 5 - Follow-up appointments have a +/- 30 day tolerance window. (ex. 6MFU may occur between 5-7 months)
 6 - Pre-SBRT labs should be done within 2 weeks prior to treatment.
 7 - Pregnancy test by urine or serum, for women who are not post-menopausal as defined in Appendix III.
 8 - Pre-SBRT procedures should be completed within 45 days of beginning treatment.
 9 - It is recommended that patients discontinue any chemotherapy one week prior to SBRT
 10 - Ideally all 5 fractions should be delivered Monday through Friday; however, treatment may be delivered over 2 weeks, as long as the patient receives at least 2 fractions per week.
 11- Pre-surgery

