SECONDARY OBJECTIVES	To evaluate rates of late (> 3 months after treatment) gastrointestinal toxicity following fractionated Linac based SBRT for pancreatic tumors. Toxicities of note include grade 2 or greater gastritis, enteritis, fistula, or ulcer and any other grade 3 or greater gastrointestinal toxicity. To evaluate local progression free survival, overall survival and metastasis-free survival rates after Linac based SBRT and subsequent resection in patients with resectable and/or borderline resectable pancreatic adenocarcinoma of the head and/or body. To develop and standardize Linac based SBRT delivery and dosimetric parameters. To estimate resection margin positivity (R0/R1) and pathologic complete response rate after neoadjuvant SBRT To evaluate pre- and post- SBRT patient reported quality of life (QOL)
TREATMENT	After 3- 4 months of chemotherapy, patients will be enrolled to a single arm trial of stereotactic body radiotherapy (SBRT) in 5 fractions given over 15 days. They will then proceed to surgery after a break of 4-6 weeks.

INCLUSION CRITERIA	
 • Age >18 years. • Karnofsky Performance Status >70% (see Appendix IV). • Histologically confirmed pancreatic adenocarcinoma of the head and/or body; at least the majority of the histopathologic specimen must be identified as adenocarcinoma. • Pancreatic tumors must be considered at least borderline resectable and/or borderline resectable at time of treatment planning. Definition of resectable and/or borderline resectable: no metastases, less than 180 degree involvement of hepatic artery, superior mesenteric artery or celiac artery • No active infection requiring hospitalization • If bilirubin > 2, patients must have a biliary stent placed prior to SBRT. • Patients must have acceptable organ and marrow function (see section “Inclusion Criteria, page 17-18). • Women who are not post-menopausal (as defined in Appendix V) should have a negative urine or serum pregnancy test. Women of childbearing potential must agree to use adequate contraception for the duration of study participation. • Ability to understand and the willingness to sign a written informed consent document. • Life expectancy > 3 months. • Patients are to have received neoadjuvant chemotherapy prior to enrollment. Approved regimens may consist of 3-4 months of gemcitabine-based chemotherapy or FOLFIRINOX. Patients will have a 2-4 week break between last chemotherapy administration and start of

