The main drawbacks of neoadjuvant treatment include: (a) possible delay of surgery due to complications of therapy, (b) the generally low response rate of advanced pancreatic cancer to multimodality treatments, and (c) the potentially higher surgical complication rate due to prior irradiation of tissue at the resection site. Encouragingly, no increase in surgical complications after neoadjuvant therapy has been reported to date (16-18).

To date, no large randomized controlled trials have studied neoadjuvant therapy for resectable and/or borderline resectable pancreatic cancer, and the sample size of existing prospective series has been small (see table II). Despite the theoretical advantages of neoadjuvant therapy, results obtained to date have shown only modest improvements compared to surgery alone. Median survival and 2-year OS for patients receiving neoadjuvant therapy range from 8-23 months and from 27-40%, respectively (19-23), compared to 11-17 months and 15-31% for surgery alone (24,25). Meanwhile, adjuvant chemoradiation (CRT) has produced a median survival of 27-44 months and 2-year OS of 53-58% (26-28). Thus, while neither neoadjuvant nor adjuvant CRT have achieved major degrees of improvement in OS, both have been demonstrated to be slightly more effective than surgery alone for pancreatic adenocarcinoma. The current prevailing management strategy, therefore, is to combine neoadjuvant chemotherapy and/or radiation, surgical resection, and adjuvant chemotherapy and/or radiation to achieve the highest possible rate of long-term survival, though no RCTs have yet been done to conclusively prove the efficacy of this regimen.

III. RATIONALE

Rationale for Radiotherapy in Treatment of Pancreatic and Periampullary Adenocarcinomas

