- The rate of treatment-related deaths during treatment, or within the first 60 days following completion of treatment, is 2 or more in the first 10 patients, or after 10 patients, 20% or more of all treated patients.
- We will also review grade IV and V adverse events deemed "unrelated" or "unlikely to be related" to verify their attribution and to monitor the emergence of a previously unrecognized treatment-related adverse event

X. DATA REPORTING / REGULATORY CONSIDERATIONS

Study Monitoring

UCCI-GI-002

Amendment 4

Page 22

4/15/2016

This study will be monitored by the University of Cincinnati DSMB and IRB. The PI will be responsible for maintaining the clinical protocol and subjects' study charts, reporting adverse events, assuring that consent is obtained and documented, and reporting the status of the trial in continuing renewals submitted to their IRB and trial monitoring group(s) as per UC protocol. There will be password-protected limited access to the database in order to maintain privacy (See Confidentiality below).

Monitoring Plan

UCCI DSMB will conduct study audits after enrollment of each 10 patients to review subjects' timely and complete enrollment, registration into the electronic database, and follow-up per study calendar. More frequent monitoring will take place as needed. Trial monitoring with subject chart and trial binder reviews will be done by the UCCI Clinical Trials office.

Data Entry and Compilation

Subject data will be documented and stored in the electronic database Oncore, the software and infrastructure being supplied by UCCI clinical trials office. Research Staff (Coordinators, Nurse, or Co-Investigators) will enter/scan subject data into Oncore, which will include:

- Eligibility or Inclusion/Exclusion Criteria
- Patient Demographics
- Pre-Study Evaluation including H & P, Allergies, and Review of Systems
- Surgical Procedures, with dates and findings (including EUS, biopsy (if needed), seed placement, and/or stent (if recommended))
- Scan dates (pancreas protocol CT)
- Treatment planning date
- Pre-Study Labs including hematology, chemistry, and tumor markers (CBC, CMP and CA 19-9)
- Radiation therapy dates and toxicities reported
- Pre-study chemotherapy records including drugs, doses, and schedules
- Surgery records including pathology reports (pathologic staging, margin status, histology), length of hospitalization and postop complications according to Appendix VI.

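### The only scheduled post-operative complication assessment falls at 4-6 weeks after radiation, the interval planned for surgery itself, and none is dated from surgery

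*Combined protocol and SAP*

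**What the plan says.** Four places in the protocol bear on this.

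- **Appendix I, study calendar.** The row "Post-op complication assessment (appendix 6") has a single mark, in the 4-6 week column. The follow-up columns are headed "Post-Radiation Treatment", so they count from SBRT. The row is blank at 4, 6, 9 and 12 months and in years 2-5.
- **Same column, other rows.** The research tube carries the footnote "11- Pre-surgery". The CT carries the footnote "If being reevaluated for resection, scans will be conducted at 4-6 weeks or as determined necessary by treating physician". A further footnote states: "Follow-up appointments have a +/- 30 day tolerance window".
- **Synopsis, Treatment.** After SBRT, "They will then proceed to surgery after a break of 4-6 weeks".
- **Section X, Data Entry and Compilation.** The surgery records to be entered include "length of hospitalization and postop complications according to Appendix VI". No period after surgery is given there.

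Section II (Background) lists among the main drawbacks of neoadjuvant treatment "the potentially higher surgical complication rate due to prior irradiation of tissue at the resection site". It adds that no such increase had been reported to date.

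**The concern.** The calendar asks one visit to serve two purposes. It is where the pre-surgery sample and the restaging scan are placed, and it is also the only point at which the post-operative form is scheduled. A visit held before the operation has nothing post-operative to record. A visit held after it has a length of observation set by scheduling and by any surgical delay. Two resected patients with the same course could have different complications on the form simply because their visits fell at different distances from surgery.

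What is at stake is even capture of a risk that the protocol names. Section III also supports the regimen partly by the absence of complications among patients resected after 6.6 Gy x 5. With so few patients, uneven capture matters. If all 20 are resected, one missed patient shifts the complication rate by 1/20 = 5 percentage points. If only 6 are resected, the minimum that Section IX accepts as feasible, the shift is 1/6 = about 17 points.

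**Working it through.** The plan gives no figure to reproduce, so the check is day arithmetic on its own schedule.

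**Inputs.** Day 0 is the last SBRT fraction.
- Surgery: 4-6 weeks (synopsis), so days 28-42.
- Visit carrying the post-operative row: 4-6 weeks (Appendix I), so days 28-42.
- Visit tolerance: 30 days either way (Appendix I), applied here to both ends of the 4-6 week range. The visit may then fall from 28 - 30 = day -2 to 42 + 30 = day 72.
- Delayed surgery: 4 weeks beyond the latest planned day, 42 + 28 = day 70. This is an illustration. Section IX has a feasibility rule on treatment delay of more than 4 weeks, so the plan itself contemplates delays of this order.

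**Formula.** Post-operative observation on the form = visit day - surgery day. Zero or less means none.

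| Case | Visit day | Surgery day | Difference (days) |
|---|---|---|---|
| Nominal, earliest visit and latest surgery | 28 | 42 | -14 |
| Nominal, latest visit and earliest surgery | 42 | 28 | +14 |
| Latest visit in tolerance, surgery at 6 weeks | 72 | 42 | +30 |
| Latest visit in tolerance, surgery at 4 weeks | 72 | 28 | +44 |
| Latest visit in tolerance, surgery 4 weeks late | 72 | 70 | +2 |

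On the nominal schedule the visit lies anywhere from 14 days before to 14 days after surgery. Using all of the tolerance gives 30-44 days of observation when surgery is on time. With surgery on day 70, even the latest permitted visit gives 2 days.

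**Next visit.** Section IV puts it at 3 months (about day 91) and Appendix I at 4 months (about day 122). Measured from surgery on days 28-42:
- 3 months: 91 - 42 = 49 to 91 - 28 = 63 days.
- 4 months: 122 - 42 = 80 to 122 - 28 = 94 days.

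Either visit comes well after surgery, but the calendar does not mark the post-operative row there.

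**The case against.** A reader might infer that the trial assesses complications before they can occur, with no post-operative observation at all. The documents do not support that. The pre-surgery footnote belongs to the research tube and the resection footnote to the CT, and the latter leaves timing to the treating physician. Nothing labels the whole visit as pre-surgical. Section XI dates the post-SBRT blood sample from surgery, so its place in this column may only be the nearest available slot. The nominal intervals for visit and surgery coincide, and the tolerance allows a visit well after the operation.

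There are also other routes for the data. Section X takes complications from the surgery records whatever the visit date, and nobody would sensibly complete a post-operative datasheet before the operation. The calendar has adverse event evaluation at every follow-up visit. Section IX records all acute events to 3 months after treatment and late events as well, whether or not they are attributed to treatment. A bleed or leak after discharge can therefore reach the database.

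A reader might also infer that the trial loses a planned estimate. It does not: the surgical complication rate is not an objective, endpoint, stopping rule or planned analysis.

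All of this stands and limits the point. None of it supplies an assessment at a defined time after surgery. Section X states no window, the adverse event tables are not tied to surgery or to resected patients, and the tolerance gives different patients different lengths of observation.

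**Conclusion.** The point holds as a scheduling inconsistency. The only scheduled post-operative complication assessment shares its interval with the planned operation, and no assessment is dated from surgery. Observation on the form can run from none to about 30-44 days with surgery on time, and to at most about 2 days with surgery on day 70. The consequence is uneven capture of a named risk, partly offset by surgery records and later adverse event evaluation. It is minor and does not affect the primary endpoint of acute grade 3 or higher gastrointestinal toxicity.

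The figures assume that the break and the visits are both counted from the last fraction, that the tolerance extends both ends of the 4-6 week range, and that a month is about 30.4 days. Appendix VI is listed in the table of contents, but the form was not in the text available for checking. If it fixes its own post-operative window, the remaining task is to bring the calendar into line with it.

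**What to change.** Reconcile Appendix I with the synopsis and Section X:

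1. Move the Appendix VI row out of the 4-6 week post-SBRT column and date it from surgery.
2. State in Section X one fixed window for every resected patient, including readmissions. One option is 30 days after surgery by chart review, updated at the existing 3- or 4-month visit. Settle first whether that visit is at 3 months (Section IV) or 4 months (Appendix I). If Appendix VI already sets a window, use that one throughout.
3. Add a sentence to Section IX that complications will be reported descriptively, with resected patients as the denominator.

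The cost is one calendar row, two sentences and slightly more chart abstraction for at most 20 patients. No new visit is needed. Calendar footnote 3 allows visits other than those at 6 and 12 months to take place at a local center, so the update may depend on records sent from there, which that footnote already requires.

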--------------------	--

EXCLUSION CRITERIA	
 • Presence of metastatic disease. • Infections requiring systemic antibiotic treatment. • Unable to understand or unwilling to sign a written informed consent document. •
PROCEDURES	Endoscopically guided fiducial placement with optional biopsies obtained at the time of fiducial placement.
STATISTICAL CONSIDERATIONS	See statistics section.

SCHEMA

Eligibility: resectable or borderline resectable adenocarcinoma of the pancreas. Definition of resectable: no metastases, less than 180 degree involvement of hepatic artery, superior mesenteric artery or celiac artery

I. OBJECTIVES

Primary Objective

- To evaluate rates of acute (within 3 months of treatment) grade 3 or greater gastrointestinal toxicity.

Secondary Objectives

- To evaluate rates of late (> 3 months after treatment) grade 2 gastritis, enteritis, fistula, and ulcer, or any other grade 3 or greater gastrointestinal toxicity
- To determine rates of local progression free survival, overall survival, and metastasis- free survival in patients with resectable and/or borderline resectable pancreatic adenocarcinoma of the head and/or body undergoing neoadjuvant SBRT
- To evaluate patient quality of life before and after Linac based SBRT.
- To evaluate the margin positivity rate and pathologic complete response rate after Linac based SBRT.
- To further develop standardization of Linac based SBRT delivery and dosimetric parameters.

II. BACKGROUND

Natural History and Management of Pancreatic Cancer

More than 40,000 individuals are diagnosed with pancreatic cancer annually in the United States. Despite aggressive combined modality treatment approaches, five-year survival of patients with pancreatic cancer is still less than 5% (1). Clearly, more innovative treatments are needed to improve survival in this group of patients.

Surgical resection is considered to be the only potentially curative treatment option (2). However, the majority of pancreatic cancer patients do not have resectable and/or borderline resectable disease at presentation. More than 85% of patients have locally advanced or metastatic disease when initially diagnosed.

Current Adjuvant Management of Resectable and/or borderline resectable Pancreatic Adenocarcinoma

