- Pathologic confirmation of malignancy. (Core biopsies during gold fiducial placement as needed or optional). Patients are encouraged but not required to have tissue banked in UCCI Tumor Bank per Tumor Bank protocol.
- Pancreas protocol CT required; if patient allergic to contrast and allergy can not be premedicated with steroids prior to IV contrast, pancreas protocol MRI will be obtained
- Baseline collection of EORTC QLQ C-30/ PAN26 QOL.

Fiducials

Treatment on this protocol requires placement of 1-5 gold (99.9% pure, 1-5 mm length, or visicoils) fiducials for targeting purposes. The fiducials will be used as surrogates for targeting the daily tumor position during treatment. The fiducials will be placed directly into the tumor and/or periphery under endoscopic ultrasound or CT guidance. When possible, clips or fiducials will also be placed in the proximal duodenum directly adjacent to the pancreatic tumor. Fiducials may be implanted prior to enrollment as this is an acceptable standard of care procedure for any patient receiving radiotherapy for pancreatic cancer.

If fiducials are not placed intraoperatively and/or prior to enrollment, placement will be done and is expected to be done on an outpatient basis. In rare occurrences when fiducials/clips cannot be placed, patients may be treated at the discretion of the PI.

Simulation

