Following Linac based SBRT, all patients will be monitored clinically and with serial imaging (CT scans and/or PET/CT if possible and as deemed necessary by the treating physician). A detailed medical history with physical examination and quality of life assessment will be performed at 4-6 weeks, 3 months, 6 months, 9 months and 1 year after radiation treatment. In years 2-5, the follow up interval will be every 3-6 months, as determined by the principal investigator. Follow up intervals may also be more frequent as indicated clinically. A complete blood count (CBC) with differential, comprehensive chemistry panel, tumor marker studies, and quality of life assessment will be performed at each follow-up interval.

GENERAL CONCOMITANT MEDICATION AND SUPPORTIVE CARE GUIDELINES

Anti-diarrheals and Anti-emetics

For symptoms of diarrhea and/or abdominal cramping, patients will be instructed to take anti-diarrheals. Additional antidiarrheal measures may be used at the discretion of the treating physician. Patients should be instructed to increase fluid intake to help maintain fluid and electrolyte balance during episodes of diarrhea. For symptoms of nausea and vomiting, anti-emetics will be given one hour prior to Linac based SBRT and for up to 5 days following Linac based SBRT on an as- needed basis. Additionally, patients will be instructed to increase fluid intake. All patients will be prescribed proton pump inhibitors (PPIs), which should begin by the start of Linac based SBRT and continue for a minimum of 6 months following Linac based SBRT.

Other Concomitant Medications

Therapies considered necessary for the patient's well being may be given at the discretion of the investigator. Other concomitant medications should be avoided except for analgesics, chronic treatments for concomitant medical conditions, or agents required for life-threatening medical problems. Specifically, if the patient is being treated with chemotherapy, it is recommended that chemotherapy be discontinued at least one week prior to initiation of Linac based SBRT and that resumption of chemotherapy be delayed for at least one week following the conclusion of Linac based SBRT. In general, prescription of these medications will be presided over by the patient's attending medical oncologist.

Supportive Care Guidelines

All commonly accepted supportive care guidelines will be used.

Use of Radioisotopes/Rad Machines

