- Creatinine clearance >60 mL/min/1.73 m² for patients with creatinine levels above institutional normal
- Ability to understand and the willingness to sign a written informed consent document.
- Patients are to have received neoadjuvant chemotherapy prior to enrollment (3-4 months). Approved regimens may consist of 3-4 months of gemcitabine-based chemotherapy or FOLFIRINOX. Patients will have a 2-4 week break between last chemotherapy

administration and start of SBRT.

- Patient must be able to have fiducials placed. If not, the tumor must be posterior and adjacent to the aorta and treatment will only be permitted at the discretion of the Principal Investigator.

Exclusion Criteria

- Children (< 18 years) are excluded because pancreatic tumors rarely occur in this age group. Furthermore, treatment requires a great deal of patient cooperation including the ability to lie still for several hours in an isolated room.
- Uncontrolled intercurrent illness including, but not limited to, ongoing or active infection (or infections requiring systemic antibiotic treatment), symptomatic congestive heart failure, unstable angina pectoris, cardiac arrhythmia, or psychiatric illness/social situations that would limit compliance with study requirements.
- Pregnant and breastfeeding women are excluded as are women of child-bearing potential who are unwilling or unable to use an acceptable method of birth control (hormonal or barrier method of birth control; abstinence) to avoid pregnancy for the duration of the study treatment. Should a woman become pregnant or suspect she is pregnant while undergoing radiotherapy in this study, she should inform her treating physician immediately.
- Women who are not post-menopausal (as defined in Appendix V) and have a positive urine or serum pregnancy test or refuse to take a pregnancy test.

VI. RISK / BENEFIT

Risk Information

It is difficult at this time to predict with confidence the percentage rate of complications from the proposed Linac based SBRT treatment. However, it is reasonable to extrapolate from the current experience with radiotherapy in and around the pancreas. Based upon prior phase I and phase II studies, we anticipate that the toxicities associated with this treatment will be acceptable.

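### The only quality-of-life form that can fall between SBRT and on-schedule surgery is not required to precede surgery, so a form completed weeks after pancreatectomy can count as the post-SBRT value

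*Combined protocol and SAP*

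**What the plan says.** Section I lists a secondary objective: "To evaluate patient quality of life before and after Linac based SBRT". The synopsis has the same aim.

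**After SBRT.** The synopsis (Treatment) plans surgery 4-6 weeks after SBRT. Section IV (Post-Linac based SBRT Follow-Up) schedules QoL at 4-6 weeks, then 3, 6, 9 and 12 months; the Appendix I calendar shows 4 months instead of 3. Footnote 5, attached to the follow-up block as a whole, reads: "Follow-up appointments have a +/- 30 day tolerance window". As I read the calendar columns, the research tubes at 4-6 weeks carry footnote 11 (Pre-surgery), and a post-operative complication assessment sits in the same column. The QoL form has no surgery anchor.

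**Before SBRT.** Section IV lists "Baseline collection of EORTC QLQ C-30/ PAN26 QOL" among the pre-SBRT items, without a day limit. In Appendix I the form sits in the Pre-SBRT column, governed by "8 - Pre-SBRT procedures should be completed within 45 days of beginning treatment". Labs have their own 2-week limit (footnote 6). Section IV (General Guidelines) and the Section V inclusion criteria place 3-4 months of chemotherapy before enrolment. On the gap, Section V says "Patients will have a 2-4 week break between last chemotherapy" and SBRT, while Section IV (Other Concomitant Medications) says "it is recommended that chemotherapy be discontinued at least one week prior to initiation of Linac based SBRT". Footnote 9 also uses one week.

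Both questionnaires use a one-week recall. Section IX contains no QoL analysis and no rule for forms completed after surgery.

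**The concern.** A before/after comparison for SBRT needs a second measurement taken after SBRT and before the next major treatment. Here that treatment is pancreatectomy, which can be expected to affect the pain, appetite, fatigue and bowel items on both questionnaires. If the first follow-up form may be completed on either side of surgery, some patients' change scores describe SBRT and others' describe SBRT plus surgery, all under one visit label.

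The baseline has a smaller version of the problem. A form completed just after the last chemotherapy dose may score nausea, diarrhoea and fatigue from chemotherapy, so that later recovery from chemotherapy is read as an effect of SBRT.

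Section III predicts that SBRT will not harm quality of life and plans a comparison with historical chemoradiation cohorts. Both uses need to know which treatments each form reflects.

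**Working it through.** **Inputs.** Surgery 4-6 weeks after SBRT, i.e. days 28-42 (synopsis). First QoL form 4-6 weeks after SBRT (Section IV, Appendix I). Tolerance 30 days (footnote 5). Chemotherapy break 14-28 days (Section V), or at least 7 days as a recommendation (Section IV, footnote 9). Recall 7 days. I count follow-up and surgery from the last fraction and take a month as 30.4375 days.

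**Reproducing the plan's own example.** Footnote 5 says that the 6-month visit may occur at 5-7 months. (6 x 30.4375 - 30)/30.4375 = 5.01 and (6 x 30.4375 + 30)/30.4375 = 6.99 months. The tolerance works as stated.

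**The 4-6 week form against surgery.**

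- Nominal windows alone: both are days 28-42. With surgery on day 28 and the form on day 42, the form is 42 - 28 = 14 days post-operative with no tolerance used.
- Upper limit with tolerance: 42 + 30 = day 72.
- Latest in-window form after surgery on day 42: 72 - 42 = 30 days.
- Latest in-window form after surgery on day 28: 72 - 28 = 44 days.
- Share of days 1-72 that fall after surgery: 30/72 = 42% to 44/72 = 61%. This is a share of permitted days, not a forecast of when forms will be completed.

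**Later forms.** The earliest 3-month form is 3 x 30.4375 - 30 = day 61; the earliest 4-month form is 4 x 30.4375 - 30 = day 92. Both come after day 42. The 4-6 week form is therefore the only one that can fall between SBRT and on-schedule surgery.

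**Baseline form.** If it follows enrolment, and chemotherapy has ended by then, it cannot be earlier than the last dose, so it falls at most 28 days before SBRT. Its recall week overlaps chemotherapy when it is completed within 7 days of the last dose: days -28 to -21 for a 28-day break, days -14 to -7 for a 14-day break.

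**Alternatives for the baseline form.**

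- Labs' 14-day limit alone: with a 14-day break, 14 - (14 - 7) = 7 days of recall overlap remain; with a 28-day break, none.
- 14-day limit plus at least 7 days since the last dose: the permitted days are -7 to 0 (14-day break) or -14 to 0 (28-day break), with no overlap.
- Day of fraction 1: 14-28 days after the last dose under the inclusion criterion, and 7 days after it if the gap were only one week, where the recall week just reaches back to the last dose.

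**The case against.** **The 4-6 week visit looks pre-operative.** Footnote 2 links its scan to re-evaluation for resection, and footnote 11 marks its research tubes Pre-surgery. That is probably the intent for part of the visit. But the post-operative complication assessment sits in the same column, and the QoL row has no mark. The intent is ambiguous, and a site following footnote 5 exactly would be compliant with a post-operative form.

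**The data are partly recoverable.** Section X records surgery and radiation dates, chemotherapy schedules and questionnaire completion. If forms are dated, they can be sorted by surgery status at analysis. This stands, but sorting cannot supply a pre-operative value that was never collected.

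**No window isolates SBRT in a single-arm study.** True. The achievable aim is narrower: to keep surgery out of the value labelled post-SBRT.

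**Stronger readings that a reader might infer.**

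- *The baseline window opens 17-31 days before the last chemotherapy dose* (45 - 28 and 45 - 14). Footnote 8 read alone allows this, but chemotherapy precedes enrolment, consent sits in the earlier Pre-Study column, and fiducial placement is the procedure expressly allowed before enrolment. It is not a realistic path.
- *The follow-up form may fall on day -2* (28 - 30). The calendar block is headed as post-radiation follow-up, so such a form would not be a follow-up form.
- *All later forms reflect surgery.* Not for unresected patients; the Section IX completion rule is met with as few as 6 of 20 patients completing therapy.
- *A few such forms could reverse the sign of the mean change.* The documents give no effect size, standard deviation or planned mean-change analysis, so this cannot be shown.

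**Conclusion.** The surgery point holds. Under the calendar as written, a form completed up to 30-44 days after pancreatectomy is an in-window 4-6 week form, and no other form can supply a value between SBRT and on-schedule surgery. A well-timed form does serve the objective; the plan does not ensure one.

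The baseline point is lesser: chemotherapy can enter through one-week recall and residual effects when the form is completed in the first week after the last dose.

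This rests on surgery occurring on schedule, on both intervals being counted from the end of SBRT, and on the baseline form following enrolment, which the calendar implies but does not state. The size can be given in days only; the documents do not support an estimate in questionnaire points. The change is worth making, but it concerns a descriptive secondary objective in 20 patients. The primary endpoint and the stopping rules do not depend on it.

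**What to change.** Add a QoL-specific footnote to Appendix I:

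1. Apply the existing Pre-surgery mark to the 4-6 week QLQ-C30/PAN26. It is completed after the last fraction and before surgery, and the 30-day tolerance does not run past the surgery date.
2. Complete the baseline form on the day of fraction 1, before treatment. Alternatively, use the 2-week limit already set for labs and require at least 7 days since the last chemotherapy dose.

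In Section IX, name this pair as the basis for the before/after SBRT change, and report later forms by whether surgery had occurred. The 2-4 week chemotherapy break and the one-week recommendation must be reconciled, as must the 3-month (Section IV) and 4-month (Appendix I) visits.

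The forms and visits already exist, and no treatment or instrument changes. The cost is a calendar footnote, a short addition to Section IX, and a few more forms that are missing or out of window.
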